Adult men and women at least 18 years of age undergoing a planned laparoscopic colectomy 300 subjects who meet all of the inclusion and exclusion criteria

1:1 randomization to VVZ-149 Injections or placebo

Study Design:

This is a multicenter, randomized, double-blind, parallel group, placebo-controlled Phase 3 study in adults undergoing a planned laparoscopic colectomy to evaluate the efficacy and safety of VVZ-149 Injections on postoperative pain. The subjects who provide informed consent, meet all the inclusion/exclusion criteria from screening to post-surgery, and report the initial Numerical Rating Scale (NRS) of ≥ 5 measured immediately after regaining consciousness from anesthesia will be eligible for randomly assigned to the VVZ-149 treatment group or the placebo treatment group.

The VVZ-149 treatment group will receive a dosing regimen of a continuous IV infusion (1,000 mg of VVZ-149 mixed into a 500 mL saline bag; 160 mg as a loading dose will be administered for 30 minutes at the beginning of infusion followed by a maintenance dose of 840 mg for 9.5 hours) over 10 hours. The placebo group will be administered a placebo in the same way as the VVZ-149 treatment group over 10 hours. All subjects will be provided with a patient-controlled analgesia (PCA) pump upon emergence from anesthesia. After the start of the study drug infusion, subjects are allowed to self-administer IV PCA of fentanyl (5 μ g IV bolus, 10 min lock-out) as needed to facilitate adequate pain relief. If the subject has been dosing with IV PCA of fentanyl but still reports the NRS score of \geq 5 upon and requests additional pain medication, the subject will be given rescue medications. The efficacy, safety, and pharmacokinetics of the VVZ-149 Injections will be evaluated at scheduled time points for 48 hours from the start of the study drug infusion.

Inclusion and Exclusion Criteria:

Inclusion Criteria

Subjects who meet all of the following criteria will be eligible to participate in the study.

- 1. Men and women must be at least 18 years of age.
- 2. Female subjects who are not pregnant or breastfeeding.
- 3. Subjects must be undergoing a planned first laparoscopic colectomy.
- 4. Subjects classified in American Society Anesthesiologist (ASA) risk class of I or II.
- 5. Subjects who report the pain intensity ≥ 5 on the NRS (NRS: Numeric Rating Scale, $0\sim10$) assessed after surgery.

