Allowed rescue medications will be provided if subjects report a pain intensity score of ≥ 5 on the NRS and require additional analgesia in addition to PCA. For the first 2 hours after the start of the study drug infusion, subjects will be allowed to receive IV fentanyl up to 2 doses in 1 hour with the first dose of 30 µg and the second dose of 20 µg at a 10-minute lockout interval. If subjects request additional rescue medications exceeding allowed fentanyl administrations for 1 hour, IV Oxycodone (Oxynorm, 2 mg, 2-hour lock-out) or Morphine (Morphine Sulfate Injection, 2 mg, 2-hour lock-out) will be given. After 2 hours from the start of the study drug infusion, IV pethidine (25 mg, 4-hour lock-out) in addition to PCA will be administered upon request in the ward. If subjects experience inadequate pain relief despite the use of PCA opioids and protocol-specified rescue medications, they will be provided appropriate pain medications at the investigator's discretion.

Pain Intensity Assessment

Pain intensity will be assessed using the NRS (0-10) at scheduled time points for 48 hours from the start of the study drug infusion. When a subject requests rescue medications, the corresponding pain

5

intensity score at the time of request will be recorded using the NRS, and the rescue medication will be administered.

Dropouts

Subjects are free to discontinue from the study at any time, without prejudice to future treatment. Reasons for withdrawal or discontinuation from the study may include the following and must be documented in the eCRF: a lack of efficacy, safety criteria (e.g., adverse events, unexpected drug reaction), pregnancy, protocol deviations, and sponsor/investigator decision. Once a subject is discontinued from the study, no data will be collected except for the safety data.

Safety Follow-Up

After discharge, subjects will be contacted for a follow-up phone interview. Subjects may visit the site at any time during the study for the postoperative care depending on the judgment of the investigator or the condition of a subject, but this follow-up visit is not included as part of this study. A total duration of the study is approximately 21 to 30 days including a safety follow-up.

Efficacy Endpoints:

The primary efficacy endpoint

Time-weighted Sum of Pain Intensity Difference (SPID) from baseline over 12 hours after the start of the study drug infusion (i.e., post-dose).

The secondary efficacy endpoints

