- Vital signs, 12-lead ECGs, and clinical laboratory evaluations per group will be summarized using descriptive statistics, and further statistical analyses will be performed regarding indices considered clinically significant as necessary.

Efficacy Analyses

The Modified Intent-to-Treat (mITT) population will be used for the efficacy analyses.

Participants who have not initiated the study drug infusion, or who do not have a baseline pain intensity score nor any post-dose pain intensity score will be excluded from the mITT population.

- To assess the robustness of the efficacy analyses, additional sensitivity analyses will be performed for the Per-Protocol (PP) population who completed at least 6 hours of study drug infusion, who have safety and efficacy data at least until Time 6 hours, and do not have any significant protocol deviations and for the Full Analysis Set (FAS) population who meet major inclusion/exclusion criteria, who have initiated study drug infusion, and who have any efficacy data after randomization.
- The primary efficacy endpoint is the time-weighted Sum of Pain Intensity Difference (SPID) for the first 12 hours postdose. The SPID for 12 hours postdose (SPID 12) will be estimated using the lineartrapezoidal rule (L x Hour) with the PI scores assigned from Time 0 to Time 12 hours postdose. SPID 12 will be summarized using descriptive statistics by treatment group, and analyzed using an analysis of variance (ANOVA) model with treatment as a main effect. The treatment effect will be tested at a two-sided alpha=0.05 level of significance. The means, standard error (SE), two-sided 95% confidence interval, and two-sided p-value from the ANOVA model will be presented. If the normality assumption is not met using Shapiro-Wilk test, a ranked ANOVA will be used to analyze the primary efficacy endpoint. The rank of the SPID 12 ranked across both treatment arms will be analyzed using a ranked ANOVA model with treatment as the main effect.

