- All secondary efficacy analyses will be carried out using two-sided tests at the alpha = 0.05 level of significance. The total number of PCA requests and the total amount of opioid consumption by PCA and/or rescue medication at pre-defined time intervals until 12 hours postdose will be summarized and analyzed using a repeated-measures ANOVA. The main effects of treatment and time and their interaction (treatment x time) will be evaluated. The proportion of subjects with ≥ 40% decrease in pain area at 6 hours post-dose compared to the maximum decrease in pain area with the pre-dose pain intensity will be summarized and analyzed by treatment group using Chisquare test (or Fisher's test if the expected cell counts with less than 5 is greater than 20%). The same method described for the primary efficacy endpoint (ANOVA) will be used to analyze the time-weighted SPID for 24 hours postdose (SPID 24).
- All exploratory efficacy analyses will be carried out using two-sided tests at the alpha = 0.05 level of significance. SPID 6 will be analyzed using an ANOVA model with treatment as the main effect. The total number of PCA requests and the total amount of opioid consumption by PCA and rescue medication for 24 (at a 6-h interval) and 48 hours (at a 12-h interval) post-dose will be analyzed using a separate repeated measures ANOVA with the main effects of treatment and time and their interaction (treatment x time).

Proportion endpoints measured per time interval will be analyzed by treatment group using Chisquare test (or Fisher's test). Additional analysis will performed using a generalized linear model with repeated measures using a logit link.

The time-to-event exploratory endpoints (time to first and second rescue medications requested by subject) will be analyzed based on the Kaplan-Meier (KM) estimate of median time (in minutes) with log-rank test and Cox proportional hazard model with treatment as a factor.

Version Date: Jan. 27, 2023

Schedule of Assessments

Period	Screen	В	aseline	e		Treatment Dosing and Assessment													
Visit	1		2															3	
Study Day	-30to-1					1							2				2 to 3		21
Time Point		Pre op	Pre dose	0h ^a	0.5h	1h	2h	4h	6h	8h	10h	12h	18h	24h	30h	36h	42h	48h ET	
Time Point Window					±5 m ±10 m			±15 m			-30 m	±15n	±1 h					+7 d	
Informed consent	X																		
Inclusion exclusion criteria	X	Xb	X ^b																
Demographics	X																		
HADS/PCS ^r		X																	
Weight and height	X																		

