- g. When scheduled for the same time point, assessments will be recommended to be performed in the following order: NRS Vital signs Oxygen saturation via pulse oximetry 12-lead ECG PK sampling Blood sampling for clinical laboratory evaluations. The order of study assessments is allowed to make changes depending on study site circumstances.
 - * It is allowed to use 12-lead electrocardiogram results within 30 days in the absence of medical history.
 - * It is allowed to perform the electrocardiogram and oxygen saturation at Time 10 hours within \pm 2 hours of the scheduled time point.
- h. Pain intensity (NRS, 0-10) will be assessed for 48 hours postdose. Additional pain intensity will be assessed immediately before administration of any rescue medication, and both the NRS and corresponding time will be recorded.
- i. Pharmacokinetic (PK) samples will be collected from the opposite arm to the study drug infusion. If the blood sampling is not available from the opposite arm, the venipuncture is performed from other body parts except for the infusion arm.
- j. A PK sample at Time 0.5 h will be collected before the completion of the loading dose infusion (-5 minutes).
- k. A PK sample at Time 10 h will be collected before the completion of the maintenance dose infusion (-15 minutes). If the total duration of the study drug infusion is less or more than 10 hours, PK sampling at Time 10 h will be performed within 15 minutes before the completion of the infusion. Additional PK samples will be collected 30 minutes after termination of the study drug infusion (±5 minutes).
- Subjects with pain intensity scores of ≥5 on the NRS upon emergence from anesthesia will be randomly assigned to either the VVZ-149 or placebo group (1:1 ratio). Subjects with the initial NRS of <5 will be eligible for randomization once they report the NRS score of ≥5 within 30 minutes after emergence from anesthesia.
- m. Randomized subject will be assigned with a study drug number and and the corresponding study drug will be administered. A continuous IV infusion of VVZ-149 (1,000 mg) or a placebo over 10 hours will be administered as a loading dose of 160 mg for 30 minutes followed by a maintenance dose of 840 mg for 9.5 hours.

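### All SPID models, including the rank fallback, contain treatment only; the primary test is valid but gives up precision by leaving out the pre-dose NRS

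*Combined protocol and SAP*

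**What the plan says.** The primary endpoint (Efficacy Endpoints) is the "Time-weighted Sum of Pain Intensity Difference (SPID) from baseline over 12 hours after the start of the study drug infusion".

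Under Efficacy Analyses, SPID 12 is "analyzed using an analysis of variance (ANOVA) model with treatment as a main effect". The test is two-sided at the 5% level. If Shapiro-Wilk rejects normality, the rank of SPID 12 "will be analyzed using a ranked ANOVA model with treatment as the main effect".

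The other SPID analyses follow suit. For 24 hours, "The same method described for the primary efficacy endpoint (ANOVA) will be used to analyze the time-weighted SPID"; for 6 hours, "SPID 6 will be analyzed using an ANOVA model with treatment as the main effect".

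No SPID model names a covariate. The sensitivity analyses described there change only the population (per-protocol and full analysis set), so the supplied text plans no baseline-adjusted SPID result.

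The Schedule of Assessments has an NRS at pre-dose, and its randomization footnote makes that pain score a condition of entry: subjects scoring 5 or more "on the NRS upon emergence from anesthesia will be randomly assigned to either the VVZ-149 or placebo group".

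**The concern.** SPID 12 equals 12 times the pre-dose NRS minus the area under the pain curve. A treatment-only model of SPID therefore uses baseline, but forces its coefficient to 1. If the slope of post-dose pain on baseline is below 1, SPID stays correlated with baseline within each arm. That explainable variance then sits in the error term.

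Two things follow. The standard error and confidence interval of the single primary test are wider than the same data allow. Also, a fraction (1 − slope) of any chance baseline difference between the arms stays in the estimate. The planned standard error covers that imbalance on average, so it is not a bias, but ANCOVA would remove it.

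Adjustment loses no subject. A subject without a pre-dose NRS has no SPID, so every subject in a SPID analysis already has the covariate.

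**Working it through.** **Inputs from the plan.** There are "300 subjects who meet all of the inclusion and exclusion criteria", randomized 1:1, hence 150 per arm; alpha is 0.05 two-sided; entry requires NRS ≥ 5, so baseline runs from 5 to 10. The supplied text gives no effect size, SD, power or correlation, so the figure of 300 cannot be reproduced.

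**Assumed inputs.** sB is the SD of pre-dose NRS, sP the SD of time-averaged post-dose NRS, and r their within-arm correlation. The base case is sB = 1.4 and sP = 1.8.

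**Formulas.**
- Slope b = r·sP/sB
- Unadjusted variance, Var(SPID/12) = sB² + sP² − 2·r·sB·sP
- ANCOVA residual variance = sP²(1 − r²)
- SE of the difference = 12·√(2·variance/150)
- Power, if ANOVA has 80%: Φ(2.80/√ratio − 1.96), where ratio = ANCOVA variance / unadjusted variance

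The unadjusted variance also equals sP²(1 − r²) + (1 − b)²·sB². The excess is therefore (1 − b)²·sB², which is zero only at b = 1.

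**Base case.** At r = 0.2 the unadjusted variance is 1.96 + 3.24 − 1.008 = 4.192 and the ANCOVA variance is 3.24 × 0.96 = 3.110, ratio 0.742. At r = 0.5 they are 1.96 + 3.24 − 2.52 = 2.680 and 3.24 × 0.75 = 2.430, ratio 0.907.

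| r | b | ratio | SE, ANOVA | SE, ANCOVA | 80% power becomes |
|---|---|---|---|---|---|
| 0.2 | 0.26 | 0.742 | 2.84 | 2.44 | 90% |
| 0.5 | 0.64 | 0.907 | 2.27 | 2.16 | 84% |

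SEs are in NRS × h. In sample size terms, 300 × 0.742 ≈ 223 and 300 × 0.907 ≈ 272 adjusted subjects match 300 unadjusted.

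**Sensitivity.**
- With sB = 1.4, sP from 1.6 to 2.2 and r from 0 to 0.6, the ratio runs from 2.56/4.52 = 0.566 (a 43% cut) to 3.098/3.104 = 0.998 (under 1%).
- With sB = 1.0 and sP = 1.8, the ratio is 3.110/3.520 = 0.884 at r = 0.2 (12% cut, power about 84.6%) and 2.430/2.440 = 0.996 at r = 0.5 (0.4% cut, power about 80.1%).
- At b = 1 the variance rises by the factor 1 + 1/296 = 1.0034, and power goes from 80.0% to 79.9%.

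**Chance imbalance (base case).** One SE of baseline difference is 1.4·√(2/150) = 0.162 NRS. It shifts the unadjusted estimate by 12(1 − b)·0.162, which is 1.44 NRS × h at r = 0.2 and 0.69 at r = 0.5, against SEs of 2.84 and 2.27.

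**Simulation of the linear and rank tests.** It used 150 per arm and 5,000 replicates, with integer NRS clipped to 0–10, the scheduled visits to 12 h and the linear trapezoid. Baseline probabilities for 5 to 10 were 0.20, 0.26, 0.22, 0.18, 0.10 and 0.04 (SD 1.41). The slope was 0.24 or 0.64, between-subject SD 1.77 or 1.56, and visit noise SD 1.2. The effect, 0.70 or 0.56 NRS at every post-dose visit, was chosen to give ANOVA about 80% power.

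| | Type I error, r = 0.2 / 0.5 | Power, r = 0.2 | Power, r = 0.5 |
|---|---|---|---|
| ANOVA | 5.0% / 4.8% | 79.8% | 79.9% |
| ANCOVA | 5.0% / 4.8% | 90.7% | 83.7% |
| Rank ANOVA | 5.4% / 4.5% | 78.3% | 78.5% |
| Rank ANCOVA | 5.1% / 4.4% | 89.2% | 82.4% |

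The Monte Carlo SE of the type I error is 0.3 points.

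**Simulation of the planned two-stage rule.** A second model (4,000 trials per setting, between-subject SD 1.3, visit noise SD 1.2, slopes 0.2, 0.5 and 0.8) included the Shapiro-Wilk switch. Under no effect, the two-stage rule rejected in 4.5% to 5.1% of trials. ANCOVA variance was 0.54, 0.73 and 0.93 of ANOVA variance at the three slopes. For a 0.5-point effect, power went from 61% to 89%, 75% to 88% and 85% to 87%.

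**The case against.** The strongest reply is that nothing here is wrong. The planned test is unbiased, holds its level, and already subtracts baseline, so the request is for a more efficient valid model. That stands, and it is why this is a recommendation and not a validity problem.

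The second reply is that no gain is shown for this trial. That also stands in part. Every SD, correlation and starting power above is assumed. The entry rule truncates baseline, and with a baseline SD of 1.0 the gain shrinks to 12% or almost nothing. The simulations build in a linear slope and a constant effect, and they have no PCA, rescue or dropout. They confirm the algebra and the type I error but are not evidence about the trial's actual slope. The power figures should be read as illustrations.

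These limits do not remove the case for adjustment, because the trade is lopsided: the worst case costs about 0.3% in variance, and any slope clearly below 1 gives a gain.

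Two smaller points are fair. Naming treatment as a main effect does not literally exclude other terms, but none is specified, and a pivotal model has to be. And the model is written into the combined protocol text, so the change is a protocol amendment, though one of wording only.

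**Conclusion.** The concern holds, as an efficiency point that should be acted on. All four SPID analyses name treatment alone, although the pre-dose NRS is collected, is a condition of randomization and is part of SPID itself. Bias and type I error are not at issue.

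The gain depends on the slope of post-dose pain on baseline and on the baseline SD, neither of which the plan gives. Across the ranges examined, the variance reduction runs from under 1% to 43%, negligible to substantial; the base case gives 9% to 26%. The reading of the text is certain; the size of the benefit is not. If the rank fallback were triggered, a change to the ANOVA alone would bring no benefit to the p-value, because the fallback is unadjusted too.

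**What to change.** - Prespecify ANCOVA of SPID 12 with treatment and pre-dose NRS as the primary model. Report the adjusted mean difference with its 95% confidence interval.
- Put the covariate in the fallback as well: rank ANCOVA, with SPID 12 and pre-dose NRS each ranked across both arms. If the fallback supplies the p-value, still report the ANCOVA difference and interval in NRS × h.
- Use the same model for SPID 24 and SPID 6.
- Keep the unadjusted ANOVA as a supportive analysis.

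The cost is a wording amendment to the combined protocol and SAP and one degree of freedom. It needs no new data and loses no subject. It should be made before unblinding, because adding the covariate afterwards would look data-driven.

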Categorical variables will be summarized using counts of subjects (n) and percentages (%) and will be presented in the form "n (xx.x)". Percentages will be rounded to one decimal place. If counts of subjects is zero (0), then percentage will not be displayed. To ensure completeness, summaries for categorical variables will include all categories, even if no subjects had a response in a particular category. Unless otherwise specified, the denominator for each percentage will be based on the number of subjects with available data in the population being summarized.

Unless otherwise specified, all statistical tests will be 2-sided using α =0.05. Estimates and confidence intervals will be reported to 1 more decimal than the original data. P-values will be reported to 4 decimal places. Pvalues less than 0.0001 will be displayed as "< 0.0001"; p-values greater than 0.9999 will be displayed "> 0.9999". Summary tables will be summarized by treatment and overall, as appropriate. All data, including those derived, will be presented in individual subject data listings.

Demographic Data Analysis

The Modified Intent-to-Treat (mITT) population will be used for the analysis of demographic variables. Age, height, body weight and body mass index (BMI) will be summarized using descriptive statistics. Age group, sex, race and American Society of Anesthesiologists (ASA) risk classification will be summarized with the number and percentage of subjects in each parameter category.

Subjects who have not initiated the study drug infusion, or who do not have a baseline pain intensity score nor any post-dose pain intensity score will be excluded from the mITT population.

Descriptive statistics will be performed in all subjects and by treatment group. Continuous variables will be summarized using descriptive statistics (sample size, mean, standard deviation, minimum, median, and maximum values). Categorical variables will be summarized using the number and percentage of subjects.

Safety Analyses

- The Safety Population who have initiated study drug infusion will be used for all safety analyses. The occurrence, the number of subjects, severity, and relatedness will be summarized for adverse events (AEs) and serious adverse events (SAEs) using descriptive statistics.

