- n. Subjects will be provided with a PCA pump for fentanyl IV infusion upon emergence from anesthesia. Once the study drug infusion has been initiated, subjects may self-administer fentanyl (5 μg IV bolus, 10-min lock-out) by pushing a button of the PCA pump for pain control.
- o. If subjects request additional rescue medications in addition to the PCA opioid, the pain intensity and corresponding time will be recorded. Upon confirming the criteria for rescue medication administration, subjects will be provided with rescue opioid within 15 minutes of the pain intensity assessment using the NRS.
- p. Adverse events identified before the study drug infusion will be documented as medical history.
- q. Safety follow-up will be conducted over the phone. If clinically significant adverse events are reported at the safety follow-up, subjects will be allowed to return to the site for the postoperative standard of care follow-up as necessary and will receive clinical laboratory evaluations, physical examination, and/or vital signs examination.
- r. The HADS and PCS questionnaires can be performed on the day before surgery (Day-1) depending on study site.

10 Version Date: Jan. 27, 2023

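### HADS and PCS are scheduled before surgery for all subjects but enter no baseline summary or model; adjusting the 12-hour PCA-request and opioid-consumption analyses for them may gain some precision

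*Combined protocol and SAP*

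**What the plan says.** The Schedule of Assessments carries one HADS/PCS row, marked once, in the pre-op column, with no restriction to a subgroup. Footnote r deals only with timing: "The HADS and PCS questionnaires can be performed on the day before surgery (Day-1) depending on study site". Either way the scores precede surgery, and randomization follows surgery.

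The supplied text does not mention them again. They are not among the primary, secondary or exploratory endpoints. Under Demographic Data Analysis the continuous variables are given as "Age, height, body weight and body mass index (BMI) will be summarized using descriptive statistics" and the categorical ones as "Age group, sex, race and American Society of Anesthesiologists (ASA) risk classification will be summarized". A general rule under General Statistical Considerations would still place them in listings: "All data, including those derived, will be presented in individual subject data listings".

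Under Efficacy Analyses, PCA requests and opioid consumption up to 12 hours are two of the four secondary endpoints. Both are analyzed by repeated-measures ANOVA, for which the text says: "The main effects of treatment and time and their interaction (treatment x time) will be evaluated". No baseline covariate is named. The exploratory 24- and 48-hour analyses use the same terms.

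**The concern.** The abbreviations are not spelled out in the supplied text. I read them as the usual anxiety-and-depression and pain-catastrophizing questionnaires. PCA use is partly behavior: the subject decides when to press the button, and rescue medication also depends on a request. Anxiety and catastrophizing are plausible drivers of both, and the trial measures them before treatment is assigned.

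If the scores do predict opioid demand, leaving them out keeps explainable between-subject variation in the error term for the treatment main effect on two secondary endpoints. With no by-arm summary, a chance imbalance in the scores would also be visible only to someone working through listings. The supplied text describes 1:1 randomization without stratification, so the design does not balance them either. If the question is left until after unblinding, any adjustment for these scores will be post hoc.

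**Working it through.** **Plan's own figure.** The text gives "300 subjects who meet all of the inclusion and exclusion criteria", randomized 1:1, hence 150 per arm. It gives no effect size, standard deviation, power or dropout rate, so 300 cannot be reproduced. Nor does it give a correlation between the scores and opioid use.

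**Inputs**
- From the documents: N = 300, 1:1 allocation, two-sided alpha 0.05 (z = 1.960).
- Assumed: 80% unadjusted power (z = 0.842). With 150 per arm this corresponds to a standardized difference of (1.960 + 0.842) × √(2/150) = 0.324.
- Assumed: multiple correlation r of the three scores with the 12-hour total, from 0.1 to 0.35.

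**Formulas**
- Residual variance ratio = 1 − r²
- Equivalent extra subjects = 300/(1 − r²) − 300
- Adjusted power = Φ[(1.960 + 0.842)/√(1 − r²) − 1.960]

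| r | 1 − r² | Extra subjects | Power |
|---|---|---|---|
| 0.10 | 0.990 | 3.0 | 80.4% |
| 0.20 | 0.960 | 12.5 | 81.6% |
| 0.30 | 0.910 | 29.7 | 83.6% |
| 0.35 | 0.8775 | 41.9 | 84.9% |

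**Cost of the covariates.** The table leaves this out. Three covariates take 3 of the 300 − 2 = 298 error degrees of freedom. The expected variance inflation is about (298 − 1)/(298 − 1 − 3) = 297/294 = 1.010, or about 0.5% on the standard error.
- r = 0: power falls from 80.0% to about 79.6%.
- r = 0.1: 0.990 × 1.010 ≈ 1.000, so the gain and the cost cancel.
- r = 0.35: 0.8775 × 1.0102 = 0.886, and power is about 84.5% rather than 84.9%.

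**Which test benefits.** The formulas describe a two-group comparison of one total per subject. With complete data this matches the treatment main effect, which compares the arms on the sum or average over intervals and is tested against between-subject error. A score that is constant within a subject, entered as a linear term, reduces that error. It leaves unchanged the within-subject error used for treatment x time.

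**The case against.** The strongest reply is that no loss has been shown. Every size above rests on an assumed correlation, and the documents point, if anywhere, toward the low end. Exclusion 13 removes unstable or poorly controlled anxiety and depression, exclusion 12 removes chronic pain, and exclusions 18 and 19 remove recent opioid use and opioid tolerance. A narrower range of scores would usually weaken any correlation, and at 0.1 the net gain is about nil. This stands, and it is why the point is conditional.

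A reader might infer more than the text supports:
- **That precision is certainly being discarded.** The documents contain no figure from which this follows.
- **That the opioid analyses are biased or their type I error inflated.** Randomization protects the unadjusted test, and its standard error already allows for chance imbalance.
- **That all the opioid tests would gain.** The treatment x time test would not.
- **That the scores disappear from the report.** The listings rule covers them. What is missing is a summary by arm.
- **That the full protocol has no use for them.** The supplied text reads like a synopsis and refers to an appendix that is not included, so a purpose may be stated elsewhere.

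One might also object that the opioid models are singled out, since SPID 12 is likewise "analyzed using an analysis of variance (ANOVA) model with treatment as a main effect". That is so. The point is limited to the opioid models because they are where these questionnaires have the most direct rationale.

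The reply does not remove the case for deciding now: the data are scheduled for all subjects, the possible cost is small and bounded, and the choice is credible only if made before unblinding.

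**Conclusion.** The point holds as a minor, optional improvement in efficiency. In the supplied text HADS and PCS have no stated use, and the 12-hour PCA-request and opioid-consumption models have no baseline covariate. For an assumed multiple correlation of 0.1 to 0.35, adjustment lowers residual between-subject variance by 1% to 12%. That is worth 3 to 42 subjects on 300 before the small covariate cost, and it applies to the treatment main effect only. The power figures also rest on an assumed 80% starting point and on all 300 subjects being analyzed. If the scores are not prognostic there is little or no gain and a loss of about 0.4 points of power. The primary endpoint is not affected, and the planned tests remain valid.

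**What to change.** Before unblinding:
- Add HADS anxiety, HADS depression and PCS total as linear covariates to the repeated-measures models for 12-hour PCA requests and 12-hour opioid consumption, keeping treatment, time and their interaction.
- Replace a missing score with its mean pooled over both arms. This is acceptable because the scores are collected before randomization, so their being missing cannot depend on treatment.
- Report the currently planned unadjusted analysis as a sensitivity analysis.
- Summarize the three scores by arm in the baseline table, and state in a sentence why the questionnaires are collected.

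The cost is SAP wording, a few lines of code, a rule for missing questionnaires and 3 degrees of freedom. No new data are needed. If the sponsor judges the scores unlikely to be prognostic, a sentence giving the reason for leaving them out of the models, together with the by-arm summary, would settle most of the point.
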